**4.2.2.2. Schedule of Activities: Exposure Day Milestone Visits**

In addition to the assessments at the interim visits described in Section 4.2.2.1, subjects must undergo testing for inhibitors at the ED milestones shown below. Testing for inhibitors may be combined with a scheduled interim visit. However, if an interim visit does *not* occur within the time windows below, the subject must return to the clinic to have the samples collected. In addition, if inhibitor development is suspected at any time during the study (e.g., the expected plasma factor VIII activity levels are not attained or if bleeding is not controlled with an expected dose), the subject will be tested for inhibitors by the central laboratory.

Activities	Visits at			
	5 ED (5±1 ED)	10 ED (10 to 15 ED)	20 ED (20 to 25 ED)	50 ED (50 to 55 ED)
Nijmegen-Modified Bethesda Assay (Inhibitor Assay)	X	X	X	X

ED = exposure day

CONFIDENTIAL

The information contained herein may not be used, disclosed, or published without the written consent of Bioverativ Therapeutics Inc.

### 4.2.2.3. Schedule of Activities: Immune Tolerance Induction

The following schedule applies to subjects who are eligible for ITI, as described in Section 10.2.5.2. The specific follow up tests to be performed following ITI depend on the outcome of ongoing testing as described in Section 10.2.7.4 and Figure 2.

Activities	Pre-ITI Assessment (ITI Day 0)	Week 2 Visit (at 2 wks ±3 days)	ITI Visits		
			Every 4 Weeks (±2 Weeks)	Every 4 Weeks (±2 Weeks)	Every 4 Weeks (±2 Weeks)
			Starting at ITI Week 4, Until negative titer is confirmed	Starting at time of confirmed negative titer, Until IR ≥66% of expected is confirmed	Starting at time of IR confirmed ≥66 % Until ITI Complete Success a OR 33 Months of treatment
Informed Consent b	X				
Physical Examination	X	X	X	X	X
Weight (kg)	X	X	X	X	X
Vital Signs c	X	X	X	X	X
Hematology d,e	X		X	X	X
Blood Chemistry e,f	X		X	X	X
rFVIII Fc Dosing g	X	X	X	X	X
Nijmegen-Modified Bethesda Assay (Inhibitor Assay) h	X	X	X	X	X
Blood Sample for Exploratory Biomarker Characterization i	X		X	X	X
FVIII Activity for Incremental Recovery j			X	X	X
Half-life Evaluation (Factor VIII activity only to be done every 12 weeks once IR ≥66% confirmed) k					X l
Anti-rFVIII Fc Antibody	X	X	X	X	X
EPD Review, including rFVIII Fc Dosing Accountability m	X	X	X	X	X
Injection Site Inspection n	X	X	X	X	X
Adverse Events	<<<ONGOING; Monitor and record at all visits; telephone call every month>>>				

CONFIDENTIAL

The information contained herein may not be used, disclosed, or published without the written consent of Bioverativ Therapeutics Inc.

Serious Adverse Events	<<<ONGOING; Monitor and record at all visits; telephone call every month>>>
Concomitant Therapy/Procedures Recording o	<<<ONGOING; Monitor and record at all visits; telephone call every month>>>

AE = adverse event; DHA=Directions for Handling and Administration; EOT = end of treatment; ET = early termination; FVIII = coagulation factor VIII; ITI = immune tolerance induction; rFVIII Fc = recombinant coagulation factor VIII Fc fusion protein; SAE = serious adverse event.

- a See Section 10.2.7.4.2 for criteria for complete success.
- b Informed consent must be obtained prior to the ITI assessments beginning at Week 0.
- c Vital signs include blood pressure, pulse rate, respiratory rate, and temperature (°C). Postdose assessments following in-clinic rFVIII Fc injections should be taken approximately 20 minutes after the end of the injection.
- d Hematology includes white blood cell count and differential, red blood cell, hemoglobin, hematocrit, and platelet count.
- e From the start of the ITI treatment period through the time of ITI complete success, samples may be drawn every other month for testing.
- f Blood chemistry includes sodium, potassium, chloride, total protein, total bilirubin, gamma glutamyl transferase, aspartate aminotransferase, alanine aminotransferase, alkaline phosphatase, blood urea nitrogen, serum creatinine, and glucose.
- g Clinic dosing is applicable only if warranted.
- h The definitive Nijmegen assay for each timepoint must be performed by the central laboratory.
- i A whole blood sample will be collected every other month during ITI treatment and at the time when the ITI outcome is declared (complete success, partial success, or failure), for exploratory assays related to immune response during ITI. Up to 10-mL (minimum 3 mL) will be collected, as allowable based on patient weight and institutional practice regarding blood draw restrictions for pediatric patients.
- j Predose samples for incremental recovery (IR) calculations are to be taken when the subject is in a non-bleeding state and after at least a 24-hour washout. Volume and units of factor infused must be calculated and recorded using the actual potency as described in Section 10.1.1 (and in the DHA). Predose sample is to be collected within 30 minutes before the start of the 50 IU/kg rFVIII Fc injection; postdose sample is to be taken 30 (±5) minutes after the start of the rFVIII Fc injection. IR assessments will be performed at the central laboratory.
- k rFVIII Fc PK assessments for half-life determination are to be performed when the subject is in a non-bleeding state and after at least a 72-hour washout. See Section 4.2.2.4.
- l The rFVIII Fc PK assessments for half-life will be performed at 12-week intervals, only after IR determinations of ≥66% of expected value on 2 consecutive months. The first rFVIII Fc PK assessment will occur 12 weeks after IR≥66% of expected value is confirmed; subsequent PK assessments will be performed every 12 weeks thereafter for subjects who have not yet achieved the criteria for ITI complete success.
- m The subject's parent/caregiver must enter dosing information into the EPD **as soon as possible after an injection and within a maximum of 7 days following the injection** (Section 10.2.4.1.4). It is recommended that parents/caregivers enter dosing information immediately after an injection.
- n Injection site inspection is only to be performed if the subject receives an rFVIII Fc injection during a clinic visit.
- o For subjects who are receiving breast milk, maternal concomitant medications will also be collected at the same time points as other concomitant therapies, unless the breast milk is derived from a source other than the mother or the mother has not consented.

CONFIDENTIAL

The information contained herein may not be used, disclosed, or published without the written consent of Bioverativ Therapeutics Inc.

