#### 4.2.2.4. Schedule of Activities: Pharmacokinetic Sampling for Half-life Determination

Subjects with a confirmed negative inhibitor titer and confirmed IR  $\geq 66\%$  of expected who have not yet achieved the criteria for ITI complete success will undergo PK evaluation for  $t_{1/2}$  every 12 weeks as described in [Figure 2](#); monitoring for inhibitor and IR will continue on a monthly basis. Subjects must not have received an injection of rFVIII Fc within at least 72 hours of the predose sample collection. The PK dose will be 50 IU/kg of rFVIII Fc. Volume and units of factor infused must be calculated and recorded using the *actual* potency as described in the DHA (see Section [10.1.1](#)).

The following Schedule of Activities applies only to subjects requiring PK assessments for determination of  $t_{1/2}$  as described in Section [10.2.7.4.2](#), Section [10.2.7.4.3](#), and Section [10.2.7.6](#).

Activities	Time in Relation to rFVIII Fc Dosing							
	Pre dose a	0	30 min ( $\pm 5$ min)	3 hr ( $\pm 10$ min)	6 hr ( $\pm 10$ min)	24 hrs ( $\pm 60$ min)	48 hrs ( $\pm 60$ min)	72 hrs ( $\pm 2$ hrs)
rFVIII Dosing		X						
PK Assessments b	X		X	X	X	X	X	X

Hr=hours; min=minutes

a Predose sample is to be collected within 30 minutes prior to the start of rFVIII Fc injection.

b Timepoints for PK assessment are measured from start of the rFVIII Fc injection.

CONFIDENTIAL

The information contained herein may not be used, disclosed, or published without the written consent of Bioverativ Therapeutics Inc.

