**Partial Success:**

The determination of partial success will be made only for subjects who have completed 33 months of ITI but who do not fulfill the criteria for complete success.

To achieve partial success, the following criteria must be met after subjects have completed 33 months of ITI:

1. Negative inhibitor titers on 2 consecutive tests within 2 months of each other

AND

15. Either of the following but not both:

- IR  $\geq$ 66% of expected

OR

- $t_{1/2} \geq$ 6 hours

If the subject has 2 negative inhibitor tests but recovery is  $<$ 66% of the subject’s baseline value (if known) [REDACTED], then the subject may remain on ITI at the discretion of the Investigator, up to a total duration of ITI of 33 months.

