5.1.2.2. Visit Windows

Screening Visit

Screening assessments must be completed within a total of 8 weeks from the start of screening activities (with the exception of informed consent, which may have occurred earlier). If more than 8 weeks have elapsed, and the patient is not enrolled in the study, then the Nijmegen inhibitor and FVIII antibody assessments must be repeated. Other screening assessments that are not completed must be completed within an additional 8 weeks, except for the collection of the genotyping sample. If necessary, a genotyping sample could be sent to the central laboratory at a subsequent interim visit.

Baseline Incremental Recovery Visit

Baseline IR Visit activities are performed as soon as practicable once all eligibility criteria were met and the patient is enrolled. This visit may be conducted along with other baseline

assessments on the same day as screening, once the patient has been enrolled, or as part of a separate baseline IR visit, as long as the patient has not yet had more than 3 doses of rFVIII Fc. Samples for IR calculations are taken when the patient is in a non-bleeding state. Baseline IR requires a washout from rFVIII Fc of at least 24 hours prior to the predose sample collection.

Treatment Period Visits

Patients on episodic or prophylactic treatment in this study participate in regular interim visits for follow up, as well as follow up at specific ED milestones. Regular interim visits were every 12 (± 2) weeks.

ED Milestone Visits

Unscheduled visits are performed at the following ED milestones to perform protocol-mandated inhibitor tests: 5 ED (± 1 ED), 10 ED (10-15 ED), 20 ED (20-25 ED) and 50 ED (50-55 ED).

ITI Visits

After a patient on episodic or prophylactic treatment is confirmed as having high- or low-titer inhibitors with poorly controlled bleeding, the patient participates in ITI visits. Pre-ITI assessment is on ITI Day 0. The first interim ITI visit is ITI Week 2 (± 3 days). Subsequent ITI interim visits are every 4 weeks until a negative titer is confirmed. After a negative titer is confirmed, interim visits are every 4 weeks until ITI Complete Success or a maximum of 33 months of treatment (see Section 7.4.9).

Patients with a confirmed negative inhibitor titer and confirmed IR $\geq 66\%$ of expected who have not yet achieved the criteria for ITI complete success, will undergo PK evaluation for $t_{1/2}$ every 12 weeks.

Post Immune Tolerance Success Visits

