7.4.9. Response to Immune Tolerance Induction (ITI)

The ITI Analysis Set will be analyzed for response to the treatment regimen. Possible treatment responses are:

Complete Success

All of the following criteria are met:

1. Negative inhibitor titers in 2 consecutive determinations at least 28 days apart
2. IR $\geq 66\%$ of baseline in 2 consecutive determinations at least 28 days apart
3. $t_{1/2} \geq 6$ hours

Partial Success

The determination of partial success will be made only for patients who have completed 33 months of ITI but who do not fulfill the criteria for complete success. To achieve partial success, the following criteria must be met after patients have completed 33 months of ITI:

- Negative inhibitor titers on 2 consecutive determinations at least 28 days apart AND
- Either of the following (but not both):
 - IR $\geq 66\%$ of baseline in 2 consecutive determinations at least 28 days apart, or
 - $t_{1/2} \geq 6$ hours

Failure:

ITI failure is defined as the inability to meet criteria for Complete Success or Partial Success after 33 months on ITI.

Early Withdrawal/ITI Ongoing:

Patients may withdraw from the study during the ITI period before reaching 33 months or complete or partial success. In addition, any patients still in the ITI sub-study at the time of EoS or interim analysis will be included in this category.

Response categories of complete success, partial success, failure, and early withdrawal will be presented overall for the ITI Analysis Set, and separately for the inhibitor subgroups specified in Section 5.1.2.5, namely:

- Patients with high-titer inhibitors
- Patients with low-titer inhibitors that meet the clinically meaningful criteria
- Patients with high-titer inhibitors or low-titer inhibitors that meet the clinically meaningful criteria

Patients fulfilling the criteria for complete success will transition to a “tapering” regimen over a minimum period of 12 weeks with the aim of starting a prophylactic rFVIII Fc regimen, as described in [Section 10.2.7.5](#) of the protocol, and will be further monitored for relapse for up to 9 months as described in [Section 10.2.7.6](#) of the protocol.

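### Half-life during ITI is scheduled only after recovery is confirmed, so on the visible text some partial-success and failure labels rest on a test that was never done

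*Protocol*

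**What the plan says.** **Outcome definitions.** Protocol 10.2.7.4.2 requires three things for complete success: negative titers twice, IR ≥66% of expected twice, and t½ ≥6 hours. Partial success is judged only after 33 months of ITI. It needs negative titers plus one of IR ≥66% or t½ ≥6 hours: "Either of the following but not both". Failure is whatever remains. SAP 7.4.9 keeps the same exclusive rule, but its IR arm asks for two consecutive determinations at least 28 days apart. The protocol's partial-success IR arm does not state a second determination.

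**Assessment schedule.** In protocol 4.2.2.3 the half-life row is marked only in the last ITI column and reads "Factor VIII activity only to be done every 12 weeks once IR ≥66% confirmed". Footnote l says that these assessments "will be performed at 12-week intervals, only after IR determinations of ≥66% of expected value on 2 consecutive months", and adds: "The first rFVIII Fc PK assessment will occur 12 weeks after IR≥66% of expected value is confirmed". Section 4.2.2.4 describes the t½ series for subjects with confirmed negative titers and confirmed IR, and states that "monitoring for inhibitor and IR will continue on a monthly basis". SAP 5.1.2.2 likewise says that such patients "who have not yet achieved the criteria for ITI complete success, will undergo PK evaluation for" t½ every 12 weeks. Protocol 10.2.7.1 and 13.3 mention t½ after a confirmed negative titer, but both refer back to the 4.2.2.3 schedule.

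**Missing values.** SAP 5.1.4 allows no imputation beyond a short list. The only ITI item on that list is a missing baseline IR. Neither document says how to classify a subject whose t½ was never measured.

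**The concern.** The partial-success definition expects some subjects to show an adequate half-life without adequate recovery. The schedule as written does not measure half-life in subjects whose recovery was never confirmed. Because failure is the residual category and partial success is an exclusive either/or, an absent t½ is silently treated as a t½ that did not reach 6 hours. That pushes subjects towards a worse label in two places: from partial success to failure, and from complete to partial success.

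ITI response serves its own secondary objective. The label also carries further, since SAP 7.4.9 summarises relapse only among complete successes.

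**Working it through.** The plan states no figure to reproduce here. The check is one date calculation and a full listing of cases.

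**Inputs**
- ITI window: 33 months (protocol 10.2.7.4.2).
- Condition for t½ testing: IR ≥66% in 2 consecutive months (4.2.2.3, footnote l).
- Lag to the first t½: 12 weeks (footnote l only).
- IR monitoring after confirmation: monthly (4.2.2.4).

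**Latest IR confirmation that still gives a scheduled t½ by month 33**
- 12 weeks = 84 days; 84 / 30.44 = 2.76 months.
- 33 − 2.76 = month 30.2.
- In weeks: 33 × 365.25 / 12 / 7 = 143.5; 143.5 − 12 = week 131.5.
- With four-week months: 33 × 4 = 132; 132 − 12 = week 120.
- Share of the window with no t½ due: 12 / 143.5 = 8.4%, or 12 / 132 = 9.1%.

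ITI visits carry a window of ±2 weeks, so month 30.2 is approximate.

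**Cases at month 33, titers negative.** The third column supposes t½ had been measured in everyone; the fourth follows the schedule. The protocol does not say whether the complete-success criteria must hold at the same time, so both readings are shown where they differ.

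| IR history | True t½ | If t½ measured | Under the schedule |
|---|---|---|---|
| Criterion never met | ≥6 h | Partial (t½ arm) | **Failure**, t½ absent |
| Criterion never met | <6 h | Failure | Failure |
| Confirmed by about month 30.2, still ≥66% | ≥6 h | Complete | Complete |
| Confirmed by about month 30.2, still ≥66% | <6 h | Partial (IR arm) | Partial (IR arm) |
| Confirmed by about month 30.2, later fell | ≥6 h | Same time: partial (t½ arm). Any time: complete | Same as column 3 |
| Confirmed by about month 30.2, later fell | <6 h | Same time: failure. Any time: partial (IR arm) | Same as column 3 |
| Confirmed after about month 30.2, still ≥66% | ≥6 h | Complete | **Partial (IR arm)**, t½ absent |
| Confirmed after about month 30.2, still ≥66% | <6 h | Partial (IR arm) | Partial (IR arm) |
| Confirmed after about month 30.2, then fell | ≥6 h | Same time: partial (t½ arm). Any time: complete | Same time: **failure**. Any time: **partial (IR arm)**. t½ absent |
| Confirmed after about month 30.2, then fell | <6 h | Same time: failure. Any time: partial (IR arm) | Same as column 3 |

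**Reading the table.** The label changes only when the true t½ is ≥6 hours and no t½ was scheduled. The t½-only arm is reached in one pattern: IR confirmed in time, then lost, with the criteria required to hold together. If they may be met at different times, that subject is a complete success and the t½-only arm is empty.

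**One or two IR determinations.** A subject with a single IR ≥66% at month 33 and no t½ is a partial success under the protocol wording and a failure under the SAP wording.

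**The case against.** **Figure 2 is not visible.** Protocol 10.2.7.4 says outcomes are assessed through that algorithm, and 10.2.7.4.3 says it may call for additional assessments. Section 4.2.2.4 also applies its sampling table to subjects who need t½ as described in 10.2.7.4.2, the section that holds the partial-success rule. Figure 2 might therefore order a t½ whatever the IR. This stands as a limit on certainty. If it does so, however, it conflicts with the word *only* in the schedule row and footnote l, and the passages still need reconciling.

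**The support is narrower than it looks.** Section 4.2.2.4 and SAP 5.1.2.2 say who will be tested. They do not say that nobody else may be, and they do not give the 12-week lag to the first test; that lag rests on footnote l alone. This stands. Even so, neither supplies a t½ for a subject without confirmed IR. The extra PK allowed in protocol 10.1 is for surgical planning or dose adjustment, not for ITI outcome.

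**The restriction may be deliberate.** A t½ series needs at least 72 hours of washout and 72 hours of sampling without further doses, about 6 days (72 + 72 = 144 hours) against daily ITI dosing, and protocol 10.2.7.3 asks that interruptions be avoided. This is a plausible reason, though the documents do not state it. It is also why no added series is proposed here.

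**Few subjects, and the data are listed.** Only titer-negative subjects who complete 33 months without complete success are concerned. Subjects still in ITI at the end of study fall into the early withdrawal/ongoing category. The SAP 7.4.9 listing would show a missing t½ for each subject. All true, but the summary table would still merge tested and untested subjects.

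**Conclusion.** The schedule and the outcome definition conflict on the visible text. A titer-negative subject who never meets the IR criterion is a failure even if his t½ is ≥6 hours. A subject whose IR is first confirmed after about month 30.2 and holds is a partial success even if his t½ is ≥6 hours. The documents give no rates of late confirmation or of IR loss, so the number affected is unknown; it is probably small and may be zero. As an illustration only, in an assumed ITI set of 10 to 20 subjects one relabelled subject moves a category by 1/20 to 1/10, or 5 to 10 percentage points. The endpoint is descriptive and secondary; the primary inhibitor endpoint is untouched.

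Three stronger readings are not supported:
- *Every titer-negative subject without confirmed IR at month 33 is wrongly a failure.* One IR ≥66% is enough for partial success under the protocol wording, and a subject with low IR and a true t½ <6 hours is correctly a failure.
- *The 12-week wait distorts complete success in general.* It can postpone the declaration, but it changes no month-33 label for a subject confirmed before about month 30, and time to ITI success is not an endpoint in either document.
- *A t½ series must be added at month 33.* That is an added procedure bearing on clinical management, and the documents do not settle it.

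The conclusion assumes that Figure 2 adds no t½ outside the 4.2.2.3 schedule and that sites follow that schedule.

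**What to change.** 1. In SAP 7.4.9, report subjects with no t½ on two separate lines, *IR met, t½ not assessed* and *IR not met, t½ not assessed*, instead of inside partial success or failure. This costs two table rows and slightly smaller counts in the named categories. It needs no new procedure.
2. Reconcile protocol 4.2.2.3 (half-life row and footnote l), 4.2.2.4 and Figure 2 with the partial-success definition in protocol 10.2.7.4.2 and SAP 7.4.9. In the same edit, settle whether the IR arm of partial success needs one determination or two, since protocol and SAP differ. This costs wording changes in both documents. Which clinical schedule is right is for the sponsor to decide.

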#### 4.2.2.4. Schedule of Activities: Pharmacokinetic Sampling for Half-life Determination

Subjects with a confirmed negative inhibitor titer and confirmed IR  $\geq 66\%$  of expected who have not yet achieved the criteria for ITI complete success will undergo PK evaluation for  $t_{1/2}$  every 12 weeks as described in [Figure 2](#); monitoring for inhibitor and IR will continue on a monthly basis. Subjects must not have received an injection of rFVIII Fc within at least 72 hours of the predose sample collection. The PK dose will be 50 IU/kg of rFVIII Fc. Volume and units of factor infused must be calculated and recorded using the *actual* potency as described in the DHA (see Section [10.1.1](#)).

The following Schedule of Activities applies only to subjects requiring PK assessments for determination of  $t_{1/2}$  as described in Section [10.2.7.4.2](#), Section [10.2.7.4.3](#), and Section [10.2.7.6](#).

Activities	Time in Relation to rFVIII Fc Dosing							
	Pre dose a	0	30 min ( $\pm 5$ min)	3 hr ( $\pm 10$ min)	6 hr ( $\pm 10$ min)	24 hrs ( $\pm 60$ min)	48 hrs ( $\pm 60$ min)	72 hrs ( $\pm 2$ hrs)
rFVIII Dosing		X						
PK Assessments b	X		X	X	X	X	X	X

Hr=hours; min=minutes

a Predose sample is to be collected within 30 minutes prior to the start of rFVIII Fc injection.

b Timepoints for PK assessment are measured from start of the rFVIII Fc injection.

CONFIDENTIAL

The information contained herein may not be used, disclosed, or published without the written consent of Bioverativ Therapeutics Inc.

